In this study, bisphosphonates will be used in much higher doses than currently recommended for treatment of postmenopausal osteoporosis, and the long-term effects of such high doses of bisphosphonates on the skeleton are not known. In order to determine if the effects of bisphosphonates are beneficial or detrimental to the skeleton, we will collect prospective data on traumatic and non-traumatic fractures. In addition, a separate companion study to S0307 will evaluate bone density and turnover in a subset of patients, and a small, limited-institution companion study of bone quality on S0307 will include bone biopsies and experimental measures of bone strength and elasticity.

Renal toxicity

As there are limited data on the long-term renal safety of high-dose bisphosphonates in healthy patients, $\underline{S0307}$ will be collecting data on renal function. Oral and short-term intravenous administration of bisphosphonates, when given according to recommended infusion doses, times, and intervals, are associated with a low risk of renal dysfunction. In a randomized comparison of monthly pamidronate (90 mg as a 2-hour infusion) versus zoledronic acid (4 mg as a 15-minute infusion), 6% to 8% of patients with breast cancer experienced deterioration of renal function during the first 12 months of bisphosphonate therapy. (12) Renal dysfunction was defined as a change in baseline serum creatinine ≥ 0.5 mg/dL or ≥ 2 times baseline value in patients with baseline normal creatinine (< 1.4 mg/dL), or a change from baseline serum creatinine ≥ 1.0 mg/dL or ≥ 2 times baseline value in patients with abnormal baseline creatinine. Rare case reports of more serious renal toxicity have been reported with long-term and/or high-dose use of pamidronate. (29-31)

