The American Society of Clinical Oncology 2003 update on the role of bisphosphonates in women with breast cancer recommends that serum creatinine be monitored prior to each dose of zoledronic acid, in accordance with FDA-approved labeling. (32) In order to be able to compare renal toxicity between all three arms of the study, S0307 will require a monthly serum creatinine in all patients for the first 6 months, increasing the creatinine assessment interval to q3 monthly at 6 months as the zoledronic acid arm moves to quarterly infusion intervals. Patients with baseline abnormal creatinine levels will be excluded from S0307. Patients who develop renal dysfunction on S0307 will have their bisphosphonate held. Reassessment of renal function will occur every 3-4 weeks, and the bisphosphonate should be reinstituted cautiously when renal function returns to baseline.

The ASCO guidelines also recommend that serum calcium, electrolytes, phosphate, magnesium, and hematocrit/hemoglobin also be monitored regularly, although the time interval is not specified. In **S0307**, these laboratory values will be monitored on a q6 monthly basis.

Osteonecrosis of the jaw

Case reports of osteonecrosis of the jaw in cancer patients on high-dose bisphosphonates have been recently published. (33,34) In one series, 36 patients receiving pamidronate or zoledronate for bone metastases (evenly split between multiple myeloma and breast cancer) presented with painful bone exposure in the mandible, maxilla or both that was unresponsive to surgical or medical treatment. (33) Approximately two-thirds of these patients were also receiving steroids, and two-thirds were receiving chemotherapy. Seventy-eight percent of the patients in this series had a dental extraction preceding the diagnosis of osteonecrosis, while the remainder developed exposed bone spontaneously.

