5.5	Patients must have a Zubrod performance status of 0 - 2 (see Section 10.5).
5.6	Patients must not be co-enrolled on protocols that have bone density as an endpoint. Patients may be registered to any other locoregional or systemic therapy breast cancer study, including cooperative group studies, as long as the protocol does not specifically exclude co-enrollment.
5.7	Patients must have a serum creatinine that is ≤ 2 times the institutional upper limit of normal and a calculated creatinine clearance of ≥ 30 ml/min within 7 days prior to enrollment. Patients with renal failure are ineligible for this study.
5.8	Patients who have previously been or are currently being treated with a bisphosphonate for bone density are eligible, as long as the bisphosphonate is discontinued at registration. No other forms of bisphosphonates, other than those prescribed in this study, may be used or planned during protocol treatment, either as an adjuvant or for the treatment of osteoporosis. (Note: This study has no placebo arm, so all patients will be receiving a bisphosphonate.)

S0307 Page 27 Revised 6/12/06 Amended 6/18/07 Amended 3/11/08

SWOG Patient	No
Patient's Initia	Is (L, F, M)
5.9	Patients must undergo a dental examination within 6 months prior to initiation of treatment per Section 7.4.
—— 5.10	A patient with skeletal pain is eligible for inclusion in the study if bone scan and/or roentgenological examination fails to disclose metastatic disease. Suspicious finding must be confirmed as benign by x-ray, MRI, or biopsy.
5.11	Patients must not have a medical history of esophageal stricture or motility disorders. Patients with a history of gastroesophageal reflux disorder (GERD) are eligible, but caution should be used when administering oral bisphosphonates.
5.12	Pregnant or nursing women may not participate due to the possibility of fetal harm or harm to nursing infants from this treatment regimen (see Section 3.0). Women of reproductive potential may not participate unless they have agreed to use an effective contraceptive method while on this trial. Women of child-bearing potential must have a pregnancy test performed within 72 hours prior to initiation of treatment (see Section 7.2).

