8.0 TOXICITIES TO BE MONITORED AND DOSAGE DELAY AND MODIFICATIONS

- 8.1 Two different versions of the NCI Common Terminology Criteria for Adverse Events (CTCAE) will be used on this study.
 - a. Serious Adverse Event (SAE) reporting

The CTCAE (NCI Common Terminology Criteria for Adverse Events) Version 4.0 will be utilized **for SAE reporting only**. The CTCAE Version 4.0 is identified and located at the CTEP website at http://ctep.cancer.gov/protocolDevelopment/electronic applications/ctc.htm. All appropriate treatment areas should have access to a copy of the CTCAE Version 4.0.

b. Routine toxicity reporting

This study will utilize the CTCAE Version 3.0 for routine toxicity reporting. A copy of the CTCAE Version 3.0 can be downloaded from the CTEP home page (http://ctep.cancer.gov). All appropriate treatment areas should have access to a copy of the CTCAE Version 3.0.

- 8.2 Bisphosphonate therapy must be held for any Grade 3 or greater toxicity (that is attributed to the bisphosphonate by the treating physician). If toxicity has not resolved within 3 months, then the patient must be removed from protocol treatment. If toxicity resolves (Grade 0-1) within 3 months, the protocol treatment should be restarted. If Grade 3 or greater toxicity reoccurs, then the patient must be removed from protocol treatment.
- 8.3 Renal Toxicity: For any increase of 0.5 mg/dL from normal baseline creatinine that is > IULN, or any increase of ≥ 1 mg/dL from an abnormal baseline creatinine that is > IULN, bisphosphonate therapy should be held, and serum creatinine must be monitored until it returns to within 10% of baseline. Once creatinine returns to within 10% of baseline, bisphosphonate therapy can be reinitiated at the same dose prior to treatment interruption.

\$0307 Page 31a Revised 7/13/09 Revised 8/30/10 Revised 4/21/11 Revised 3/28/14

For patients in the zoledronic acid arm with an increased creatinine, consider increasing the infusion duration to 30 minutes in subsequent cycles.

Grade 3 or higher creatinine elevations (> 3 x the institutional upper limit of normal) that is attributed to the bisphosphonate by the treating physician will require removal of the patient from protocol treatment.

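### Protocol Sections 8.2 and 8.3 give opposite instructions for a drug-attributed Grade 3 creatinine rise that resolves, and the first hold trigger in 8.3 cannot be met as literally worded

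*Combined protocol and SAP*

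**What the plan says.** **Section 8.2.** Drug is held for any toxicity of Grade 3 or higher that the treating physician attributes to it. Then: "If toxicity resolves (Grade 0-1) within 3 months, the protocol treatment should be restarted". A toxicity that has not resolved by 3 months, or a second one of Grade 3 or higher, leads to removal.

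**Section 8.3, hold rule.** There are two triggers. The first begins "For any increase of 0.5 mg/dL from normal baseline creatinine that is > IULN". The second is a rise of at least 1 mg/dL from an abnormal baseline, followed by the same qualifier. Drug may resume at the same dose once creatinine is within 10% of baseline.

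**Section 8.3, last paragraph.** A creatinine elevation of Grade 3 or higher, defined as more than 3 times the IULN and attributed to the drug, "will require removal of the patient from protocol treatment".

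**Elsewhere.** Section 7.12b lists unacceptable toxicity as a reason for removal and points to Section 8.0 as a whole. Section 8.6 names contacts for dose-modification questions.

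**Section 2.0 background.** It says "Patients with baseline abnormal creatinine levels will be excluded from S0307", that drug is resumed when renal function is back at baseline, and, of calcium, electrolytes, phosphate, magnesium and hematocrit/hemoglobin, that "these laboratory values will be monitored on a q6 monthly basis". Section 5.7, by contrast, reads "Patients must have a serum creatinine that is ≤ 2 times the institutional upper limit of normal", together with a calculated clearance of at least 30 ml/min. Section 7.9 and the study calendar place the other laboratory tests at Months 2, 4 and 6 and then every 3 months.

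**The concern.** Sections 8.2 and 8.3 are adjacent paragraphs of the part of the protocol that sites use to hold, restart or stop drug. On an attributed Grade 3 creatinine rise they prescribe opposite outcomes for the same patient. The sentence meant to catch smaller rises does not say which value its threshold applies to.

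Section 2.0 makes a three-arm comparison of renal toxicity a purpose of the creatinine monitoring. Holds and removals determine drug exposure, so an unclear rule affects patient safety first and the interpretation of exposure and renal events second.

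**Working it through.** The plan states no figure that could be reproduced here. The check sets the rules side by side. The documents give no numerical IULN, so 1.0, 1.2 and 1.4 mg/dL are assumed as a range.

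**(a) Attributed Grade 3 creatinine elevation**

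The threshold in 8.3 is 3 × IULN, which is 3.0, 3.6 or 4.2 mg/dL over the assumed range. For a patient above it, with the rise attributed to the drug:

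| Course | Section 8.2 | Section 8.3 |
|---|---|---|
| Grade 0-1 within 3 months, first episode | restart | remove |
| Not resolved by 3 months | remove | remove |
| Resolves, then Grade 3 or higher again | remove at the second episode | remove at the first |

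The two agree only when the toxicity does not resolve. They part at the first episode that resolves. Section 8.2 makes no exception for creatinine, 8.3 does not refer to 8.2, and 7.12b points to both.

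**(b) First hold trigger in 8.3**

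Let B be the baseline creatinine, C the on-study value and U the IULN. A normal baseline means B ≤ U. The stated rise is taken as C − B ≥ 0.5.

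- Clause describes the baseline: B ≤ U and B > U are both required. No patient can meet this.
- Clause describes the on-study value: B ≤ U, C − B ≥ 0.5 and C > U. This can be met.

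Example: B = 0.9, C = 1.5, so C − B = 0.6. Since 1.5 exceeds 1.0, 1.2 and 1.4, the second reading gives a hold at every assumed IULN. The first reading never does.

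The second trigger does not settle the matter. Taking abnormal to mean above the limit, B > U already holds, and C ≥ B + 1 then exceeds U as well. The qualifier adds nothing there on either reading.

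**(c) Section 2.0 against the sections that sites follow**

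- Entry: creatinine above 1 and up to 2 times the IULN, with adequate clearance, is excluded by 2.0 and admitted by 5.7. The group is not empty. By the Cockcroft-Gault formula in 7.3, an assumed woman aged 55, weighing 75 kg, with creatinine 1.8 mg/dL has (140 − 55) × 75 × 0.85 / (72 × 1.8) = 41.8 ml/min.
- Resumption: return to baseline (2.0) against within 10% of baseline (8.3).
- Other laboratory tests to Month 36: Months 2, 4, 6 plus Months 9 to 36 by threes is 3 + 10 = 13 draws (7.9 and calendar). Six-monthly is 6 draws (2.0).
- Creatinine timing does not conflict: Months 2 to 6 plus Months 9 to 36 by threes is 5 + 10 = 15 draws throughout.

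**The case against.** The best answer on (a) is that 8.2 is general while 8.3 is headed renal toxicity and has its own explicit Grade 3 rule, so on ordinary principles the specific provision prevails. Section 8.6 also gives sites someone to ask. On (b), only one reading yields a usable rule, and a sensible site would adopt it. On both, the time for action has largely passed. Accrual closed on 1 February 2010, and under 8.4 the last zoledronic acid dose comes no later than 36 months after registration, that is by about February 2013. The page carrying the end of 8.3 shows a revision date of 28 March 2014.

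Much of this stands, and it limits the weight of the point. It does not remove the defect. Section 8.2 is written for any toxicity of that grade, and nothing in the text makes 8.3 an exception. The amendment history suggests how this may have arisen: the March 2008 change to 8.2 replaced removal with hold and restart for toxicity in general, and its description mentions no renal exception. Revision #5 was meant to clarify the levels of creatinine increase in the first sentence of 8.3, yet the current sentence still leaves the qualifier unattached. That a reader can supply the missing instruction does not mean the protocol gives it.

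**Conclusion.** Section 8.0 is wrong as written in two places: opposite instructions for one defined situation, and a hold trigger that is impossible on one reading and workable only on another that the text does not state. The size is modest. Design quantities are untouched, and the Grade 3 conflict is confined to attributed elevations that resolve. The example in (b) rests on the assumed IULN range; the logical point does not.

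Four stronger readings are tempting and are not supported.

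- A reader might join "Renal dysfunction was defined as a change in baseline serum creatinine" to "Patients who develop renal dysfunction on S0307 will have their bisphosphonate held" and infer that Section 2.0 sets a numerical hold rule, including a doubling criterion, which 8.3 breaches. The definition belongs to the account of a cited comparison of pamidronate with zoledronic acid. The S0307 sentence gives no number.
- A reader might treat entry and laboratory frequency as live contradictions for sites. Section 5.7, the abnormal-baseline trigger in 8.3 and the Fast Fact Sheet's creatinine limit agree with one another, as do 7.9 and the calendar. Only background text is out of step.
- A reader might cite the October 2009 memorandum on missed magnesium and phosphate tests. It does not attribute the deficiencies to conflicting schedules, and notes that these tests may not be in an institution's routine chemistry panel.
- A reader might conclude that patients with the same result were treated differently. That is foreseeable, but the documents show no instance. The Serum Creatinine Reporting Form collects every value with its upper limit, so renal toxicity can still be classified under a single definition. Exposure is the part that the rules could have affected.

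**What to change.** - Reconcile 8.2 and 8.3 by stating which governs an attributed creatinine elevation of Grade 3 or higher, with a cross-reference.
- Reword the first trigger in 8.3 so that it says whether the IULN condition applies to the baseline or to the on-study value.
- As housekeeping, reconcile the Section 2.0 statements on abnormal baseline creatinine, resumption and six-monthly laboratory tests with 5.7, 8.3, 7.9 and the calendar.

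The clinical team decides which rule is right in each case.

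The cost is a few sentences of protocol text and a short memorandum. No change to sample size, data collection or the analysis of disease-free survival is needed. Because study treatment should be over, the practical benefit now is a record of which rule was intended, so that removals, holds and exposure can be read correctly in the renal safety report.

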10.0 CRITERIA FOR EVALUATION AND ENDPOINT DEFINITIONS

- 10.1 Invasive Recurrence: Appearance of any new invasive lesions during or after protocol treatment. Whenever possible recurrences should be documented histologically. A new diagnosis of ipsilateral or contralateral DCIS without an invasive component is not considered to be a recurrence.
- 10.2 Sites of first invasive recurrence: All sites of invasive disease documented within 30 days of first documentation of invasive recurrence.
- 10.3 Disease-Free Survival: Time from date of registration to date of first observation of recurrence or death due to any cause. Patients last known to be alive who have not experienced recurrence of disease are censored at their last contact date.
- 10.4 Overall Survival: Time from date of registration to date of death due to any cause. Patients last known to be alive are censored at their last contact date.
- 10.5 Performance Status: Patients will be graded according to the Zubrod performance status scale.

POINT	DESCRIPTION
0	Fully active, able to carry on all pre-disease performance without restriction.
1	Restricted in physically strenuous activity but ambulatory and able to carry out work of a light or sedentary nature, e.g., light housework, office work.
2	Ambulatory and capable of self-care but unable to carry out any work activities; up and about more than 50% of waking hours.
3	Capable of limited self-care, confined to bed or chair more than 50% of waking hours.
4	Completely disabled; cannot carry on any self-care; totally confined to bed or chair.

11.0 STATISTICAL CONSIDERATIONS

- 11.1 At registration, patients will be randomized to receive zoledronic acid (Z), clodronate (C) or ibandronate (I) for three years. Simple randomization will be used with equal allocation to the treatment groups due to the large sample size planned.
- 11.2 The final target accrual is 5,400 patients distributed as follows: 2,000 zoledronic acid, 2000 clodronate, and 1,400 ibandronate. After the trial began, plans to market ibandronate in North America were abandoned so we have concentrated remaining accrual in the other two arms. Nonetheless, ibandronate remains of interest since it is a highly active oral agent and may provide an effective treatment where IV administration would be difficult. The expected accrual rate currently is 286 per month. The former accrual target was 4,500 patients equally allocated to the three groups with an assumed accrual rate of 63 per month. That accrual goal was established in 2007 under CTEP guidelines for reassessing accrual at one year. Accrual increased dramatically after that reassessment which then shortened the trial duration and lowered power. Consequently, the accrual was increased to 5,400 to restore power to desired levels. The original sample size goal was 6,000 patients over a four year accrual period or 125 per month. The final sample size is 5,400 accrued over an approximate four year period. At the end of the accrual period, there will be an additional 5 years of follow-up before the scheduled final analysis. However, all patients will be followed for 10 years from randomization to assess long-term outcomes.

- 11.3 The primary outcome is disease-free survival (see Section 10.3). The complete Statistical Analysis Plan may be found in Appendix 19.4 as a separate document. Only a summary is provided here. The primary analysis is a log-rank survival comparison of the three groups followed by three pairwise comparisons if the overall omnibus test is statistically significant at the designated level. The analysis will be stratified by time period of randomization (3 Arms versus 2 Arms) as described in the S0307 Statistical Analysis Plan (see Appendix 19.4). Each pairwise comparison is performed at the same α level as the overall comparison. Given that the overall comparison is significant, this preserves the experiment-wise error rate at the designated level. (64) Since three active treatments are being compared, we assume that clodronate is the "standard" treatment that the newer agents are being compared against. Clodronate and placebo are being directly compared in NSABP trial B-34. A secondary analysis of overall survival (see Section 10.4) will also be performed. Stratified Cox regression will be used to estimate the hazard ratios and confidence intervals for the treatment comparisons, both unadjusted and adjusted for tumor and patient characteristics related to prognosis.
- 11.4 The sample size targets assumes a cumulative α =0.05 for the omnibus comparison of the three groups. The least effective treatment is assumed to have disease-free survival of 80% at 5 years. The least effective treatment compared to the most effective treatment is assumed to have a hazard ratio of 1.25. The third treatment is varied from 1.00 to 1.25. Power is computed by simulation assuming exponential distributions, 4.17 years of accrual, and an additional 5 years of follow-up. Power of the omnibus test depends on the distribution of the three hazard ratios with power lowest if the middle group is midway between the high and low groups (i.e. HR=1.125). Given a significant omnibus test, pairwise comparisons will be performed..

HR = 1.0, 1.25, 1.25 (zoledronic acid (Z) = ibandronate (I) > clodronate (C))

	Power	Power	Power	Power
	Omnibus	Z vs C	I vs C	Z vs I
Equal allocation (n=1500, 1500, 1500)	86%	78%	78%	NA
Equal allocation (n=1800, 1800, 1800)	91%	86%	86%	NA
Unequal allocation (n=2000, 1400, 2000)	93%	89%	84%	NA

HR = 1.0, 1.0, 1.25 (zoledronic acid > ibandronate = clodronate)

	Power	Power	Power	Power
	Omnibus	Z vs C	I vs C	Z vs I

If the omnibus analysis is statistically significant at an interim analysis, then pairwise comparisons will be performed using the same alpha level. If one treatment group is clearly superior to the other two, consideration will be given to stopping the trial. If one treatment group is clearly inferior to the other two, consideration will be given to stopping accrual to that arm (if accrual is incomplete) or having patients change to other treatments (if treatment is ongoing). The exact decision will depend on the full information available including adverse events and efficacy. It is also possible that the interim analysis will show that it is unlikely the trial will find a statistically significant difference among the three groups. Conditional power will be conducted at each interim analysis to determine the probability of finding a significant difference at the end of the trial. Additionally, the hazard ratio of the worst treatment versus the best treatment will be computed with a 99% confidence interval. If the upper limit of the confidence interval is lower than the alternative hypothesis of HR=1.25, consideration will be given to stopping the trial due to futility. If it is determined that there are justifiable reasons for early termination, a recommendation will be made to the Data and Safety Monitoring Committee.

Year	Analysis	Percent of Events (n=1,314)	Alpha Level for Test	Cumulative probability
4	Interim 1	31%	0.0010	0.0010
5	Interim 2	46%	0.0012	0.0022
6	Interim 3	60%	0.0068	0.0077
7	Interim 4	74%	.0158	0.0158
8	Interim 5	87%	.0265	0.0265
9	Final	100%	.0391	0.0500

- 11.6 A sample of 2,000 patients on an arm is sufficient to estimate the probability of specific toxicities to within at least \pm 0.022. A difference in toxicities of 0.05 between two arms can be detected with 90% power (2-sided α =0.05) if the mean prevalence of the adverse event is 20%.
- 11.7 Percent of patients with bone as a site of first recurrence will be compared. Approximately 4% of all randomized patients are expected to have bone as the site of first recurrence. Bone is the site of first metastases in 40% of the patients who become metastatic. If two-thirds of the patients have measured markers (e.g. PTHrP, serum N-teleopeptide levels) and the markers are dichotomized at the median, then a difference of 0.024 (0.052 vs. 0.028) in bone recurrence rates in all patients could be detected with 90% power (2-sided α =0.05).
- 11.8 A Data and Safety Monitoring Committee will oversee the conduct of the study. The Committee consists of four members from outside of the Southwest Oncology Group, three Southwest Oncology Group members, three non-voting representatives from the National Cancer Institute (NCI), and the Group Statistician (non-voting). The members of this Committee will receive confidential reports every six months from the Southwest Oncology Group Statistical Center, and will meet at the Group's bi-annual meetings as necessary. The Committee will be responsible for decisions regarding possible termination and/or early reporting of the study

12.0 DISCIPLINE REVIEW

There will be no discipline review for this study.

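### Section 11.7 pairs a 0.024 difference with 90% power, which fits the former 4,500-patient target; at the current 5,400 the same difference has about 95–96% power

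*Combined protocol and SAP*

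**What the plan says.** Section 11.7 gives the power for comparing bone as site of first recurrence between patients with high and low marker values (PTHrP, serum N-telopeptide). Its inputs are:

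- the overall event rate: "Approximately 4% of all randomized patients are expected to have bone as the site of first recurrence";
- the share of patients with data: "If two-thirds of the patients have measured markers";
- the grouping: "the markers are dichotomized at the median";
- a two-sided alpha of 0.05.

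Its conclusion is "then a difference of 0.024 (0.052 vs. 0.028) in bone recurrence rates in all patients could be detected with 90% power". The section does not state a total sample size or the form of the test.

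Section 11.2 fixes the size of the trial: "The final target accrual is 5,400 patients distributed as follows: 2,000 zoledronic acid, 2000 clodronate, and 1,400 ibandronate". It also records the target that this replaced: "The former accrual target was 4,500 patients equally allocated to the three groups".

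**The concern.** Section 11.7 fixes every input except the total number of patients, and Section 11.2 supplies that. Putting 5,400 into the calculation does not return 90% power for 0.052 versus 0.028. Putting 4,500 in does. The section therefore seems to carry a figure from the earlier target beside sections rewritten for the current one.

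What is at stake is limited. Section 11.7 holds the only power statement for the association of the markers with bone recurrence (part of Objective 1.5); the SAP in Appendix 19.4 gives none. A reader who takes it at face value would think the marker analysis less sensitive than the stated design makes it, and could not reproduce the figure from that design.

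**Working it through.** **Inputs.** From Section 11.7: p1 = 0.052, p2 = 0.028, d = 0.024, mean rate 0.04 (the average of the two, agreeing with the stated 4%), two-sided alpha 0.05, two-thirds measured, median split. From Section 11.2: N = 5,400 now, 4,500 formerly.

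**Group size.** n per group = N × (2/3) × (1/2) = N/3. This gives 1,500 at N = 4,500 and 1,800 at N = 5,400.

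**Formula, no continuity correction (pooled variance under the null).**

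z = [d√n − 1.960 × √(2 × 0.04 × 0.96)] / √(p1(1−p1) + p2(1−p2)), and power = Φ(z).

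- 1.960 × √0.0768 = 0.5432
- √(0.049296 + 0.027216) = √0.076512 = 0.2766

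**Reproducing the plan's figure, n = 1,500.** z = (0.024 × 38.730 − 0.5432)/0.2766 = (0.9295 − 0.5432)/0.2766 = 1.397, so power is 91.9%.

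**Current design, n = 1,800.** z = (0.024 × 42.426 − 0.5432)/0.2766 = (1.0182 − 0.5432)/0.2766 = 1.717, so power is 95.7%.

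**With continuity correction.** Replace n by n′ = (n − 1/d)²/n, where 1/d = 41.67.

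- n = 1,500: n′ = 1,458.3²/1,500 = 1,417.8, z = 1.303, power 90.4%.
- n = 1,800: n′ = 1,758.3²/1,800 = 1,717.6, z = 1.632, power 94.9%.

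**Difference detectable with 90% power around a 4% mean.** Solve d√n = 1.960 × √0.0768 + 1.2816 × √(p1(1−p1) + p2(1−p2)) with rates 0.04 ± d/2. At n = 1,800 without correction: (0.5432 + 0.3546)/42.426 = 0.0212.

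| Total N | n per group | Power for 0.052 vs 0.028 (corrected / uncorrected) | Difference at 90% power (uncorrected / corrected) |
|---|---|---|---|
| 4,500 (former target) | 1,500 | 90.4% / 91.9% | 0.0232 / 0.0238 |
| 5,400 (Section 11.2) | 1,800 | 94.9% / 95.7% | 0.0212 / 0.0217 |
| 5,600 (expected, Appendix 19.4) | 1,867 | 95.6% / 96.3% | 0.0208 / 0.0213 |
| 6,000 (original target) | 2,000 | 96.7% / 97.2% | 0.0201 / 0.0206 |
| 6,097 (accrual reported in the AZURE memorandum) | 2,032 | 96.9% / 97.4% | 0.0199 / 0.0204 |

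**Choice of test.** At 1,800 per group, unpooled variance gives 95.7%, the arcsine approximation 96.0% and Fisher's exact test 95.3%. None comes near 90%. At 1,500 per group the same three give 91.9%, 92.4% and 91.0%.

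**Working backwards.** 90% power for 0.024 needs 1,399 per group uncorrected or 1,482 corrected. Multiplying by three gives N = 4,197 or 4,446, the latter close to 4,500. At N = 5,400 those group sizes would mean that 2 × 1,399/5,400 = 52% to 2 × 1,482/5,400 = 55% of patients had markers, not two-thirds.

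**How it may have arisen.** The change memoranda at the front of the document are used here only as explanation. The amendment that lowered the target to 4,500 replaced the statistical section with new Sections 11.1 to 11.8, so 11.7 was issued then. Revision #5, which raised the target to 5,400, lists 11.1, 11.2 and 11.4 to 11.6 as updated, and not 11.7. The mismatch itself lies within the current text, between 11.2 and 11.7.

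**The case against.** The strongest reply is that the sentence misleads nobody to the trial's cost. A difference of 0.024 can be detected with at least 90% power under the current target, so the statement is conservative. Section 11.6 next door also uses 90% loosely. It was updated for 2,000 per arm, yet a 0.05 difference around a 20% prevalence (0.225 versus 0.175) has about 97.7% power with 2,000 in each of two arms. On that reading 90% is a nominal floor.

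Further, 11.7 states no N, so the 4,500 basis is inferred. The inputs are also soft, since marker submission is optional and the 4% is approximate. As assumed variations at N = 5,400: with 55% measured, power is 90.1% to 91.6%; with 60%, 92.5% to 93.7%. With an overall rate of 3.5% and the same relative effect it is 91.6% to 92.9%, and with 3.0%, 86.6% to 88.6%. The 4% rate may itself date from the earlier design, and the documents do not allow it to be recomputed.

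Much of this stands as a limit on importance. The direction is safe, the objective is secondary, accrual has closed, and no alpha level, stopping rule or analysis method depends on the figure. It does not make the figure right. Section 11.7 pairs a specific difference with a specific power under its own two-thirds and 4% assumptions, and under those assumptions the design in 11.2 does not give that pair. If lower marker uptake or a lower event rate is expected, the section should say so.

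**Conclusion.** The concern holds. Under Section 11.7's own assumptions and the 5,400 patients of Section 11.2, power for 0.052 versus 0.028 is about 95–96%, some 5 to 6 points above the stated 90%. Equivalently, the difference detectable with 90% power is about 0.021 to 0.022, roughly a tenth smaller than the stated 0.024.

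The arithmetic is firm. That the figure was carried over from the 4,500-patient design is an inference, though a well-supported one: the corrected detectable difference at 4,500 is 0.0238, which rounds to the printed 0.024, and the change history fits. The point is minor. The error understates what the marker analysis can do, and the primary design is untouched.

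**What to change.** Rewrite the power sentence in Section 11.7 for 5,400 patients and state that N: 3,600 with markers, 1,800 per group. Give either about 95% power for 0.052 versus 0.028, or 90% power for a difference of about 0.021 to 0.022 (roughly 0.051 versus 0.029). Name the test and whether a continuity correction was used, and keep the result explicitly conditional on two-thirds being measured and a 4% overall rate. If the sponsor now expects a different uptake or rate, use those values and say so.

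The cost is one sentence. Conduct, data collection and the analysis methods do not change.
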